6.3 Reporting Requirements for Safety Parameters

6.3.1 Study Reporting Period for Adverse Events

All AEs that occur after a subject has signed the written informed consent form through the 90-Day Post Last Dose Visit must be reported by the investigator.

Any new sign or symptom, disease, or other untoward medical event that occurs after the subject/legal representative signs the informed consent form must be reported by the investigator as an AE in the same way as AEs that occur after the subject receives investigational product.

6.3.2 Study Reporting Period for Serious Adverse Events

The reporting period for SAEs is the period immediately following the time that written informed consent is obtained through the 90-Day Post Last Dose Visit. After the initial SAE report the investigator is required to follow each subject proactively and provide further information on the subject's condition to MedImmune Patient Safety.

All SAEs should be followed up to resolution by the investigator, even if this extends beyond the study reporting period. Resolution of an SAE is defined as the return to baseline status or stabilization of the condition with the expectation that it will remain chronic.

At any time after completion of the study, if an investigator or qualified designee becomes aware of an SAE that is suspected by the investigator or qualified designee to be related to investigational product, the event should be reported to MedImmune Patient Safety.

6.3.3 Notification of Sponsor of Serious Adverse Events

Within 24 hours of identifying an SAE, regardless of the presumed relationship to the investigational product, the investigator or qualified designee must complete the SAE Report Form and fax to MedImmune Patient Safety or designee (ie, contract research organization).

MedImmune contact information:

Patient Safety
MedImmune
[name]
[contact]

MedImmune will provide international fax numbers to the sites in countries outside of the US.

MedImmune, as sponsor of the study is responsible for reporting certain SAEs as expedited safety reports to applicable regulatory authorities, ethics committees, and participating investigators, in accordance with ICH Guidelines and/or local regulatory requirements. MedImmune may be required to report certain SAEs to regulatory authorities within

7 calendar days of being notified about the event; therefore, it is important that investigators submit additional information requested by MedImmune as soon as it becomes available.

Investigators should provide all available information at the time of SAE Report Form completion. Investigators should not wait to collect additional information to fully document the event before notifying MedImmune Patient Safety of an SAE. When additional information becomes available, submit a follow-up SAE Report Form (separate from the initial report form) with the new information. Any follow-up information to an SAE also needs to be provided to MedImmune Patient Safety within 24 hours of learning of the new information.

6.3.4 Notification of Institutional Review Board or Independent Ethics Committee of Serious Adverse Events

The investigator must comply with the applicable regulatory requirements related to the reporting of SAEs to the IRB/IEC. The IRB/IEC must be informed in a timely manner by the investigator of SAEs occurring at their site during the study. The sponsor will submit information on serious unexpected and related events to any EU IECs. Investigators must also submit safety information provided by MedImmune to the IRB/IEC as detailed in Section 10.1 and Section 10.2.

6.3.5 Other Events Requiring Immediate Reporting

6.3.5.1 Pregnancy and Overdose

The following events are not necessarily considered to be AEs but are considered immediately reportable events and are required to be reported in real time (i.e., within 24 hours of learning about the event) to MedImmune Patient Safety using the Fax Notification Form:

1. Pregnancy
2. Investigational product overdose (whether or not the overdose is associated with an AE or SAE)

Subjects who become pregnant during the study period must not receive additional doses of investigational product. If the subject requests to know which treatment she received, this information will be provided to her. After obtaining the subject's consent, the subject will be followed for the duration of the pregnancy. A pregnancy should be followed for outcome and any premature terminations reported. In addition, the health status of the mother and child, including date of delivery, and the child's gender and weight should be reported to MedImmune Patient Safety after delivery.

6.3.5.2 Other Protocol-specific Events

The following events are also considered IREs and must be reported *within 24 hours* to MedImmune Patient Safety using the Fax Notification Form:

1. Any withdrawal of consent during the study
2. Any event resulting in discontinuation of investigational product

6.3.5.3 Hepatic Function Abnormality

Hepatic function abnormality (as defined in Section 6.1.3.1) in a study subject, with or without associated clinical manifestations, where the etiology is unknown, is required to be reported as “hepatic function abnormal” within 24 hours of knowledge of the event to MedImmune Patient Safety using the Safety Fax Notification Form (see Section 6.3.3 for contact information). The investigator shall review the data with the medical monitor. The investigator should use clinical judgment to establish the cause based on local standard of care and follow the subject by conducting testing as clinically indicated. If, after appropriate workup, in the opinion of the investigator, the underlying diagnosis for the abnormality remains unexplained, discontinuation of dosing for this subject should be considered.

Each reported event of hepatic function abnormality will be followed by the investigator and evaluated by the sponsor. If the etiology of the event remains unconfirmed and/or is considered related to investigational product (see Section 6.2.2), a prompt cumulative review of safety data and the circumstances of the event in question will be conducted and assessed by the MedImmune safety review committee (see Section 6.4) to determine whether continued dosing of current study subjects and/or study entry should be interrupted, whether the protocol will be modified, or whether the study will be discontinued permanently. Review and approval by the MedImmune safety review committee is required for resumption of subject dosing or study entry in the event that the study is interrupted. Where applicable, regulatory authorities and IRBs/IECs will be notified of any actions taken with the study.

6.3.5.4 Hepatitis Reactivation

Any event of hepatitis reactivation must be reported immediately (i.e., within 24 hours of learning about the event), regardless of the amount of time that has passed since the subject’s last MEDI-551 dose.

6.3.5.5 Infusion-related Reactions

Any infusion-related reaction of a study subject with the investigational product causing permanent discontinuation of dosing with investigational product, with or without associated

AEs/SAEs, is required to be reported within 24 hours of knowledge of the event to MedImmune Patient Safety or designee using the Fax Notification Form (see Section 6.3.3 for contact information). An infusion reaction does not automatically make an AE serious, but if the consequences of the reaction are serious, for example death or hospitalization, the event is serious and must be reported as an SAE (see Section 6.2.4 and Section 6.3).

6.3.5.6 Progressive Multifocal Leukoencephalopathy

Any suspected case of PML should be immediately reported (i.e., within 24 hours of learning about the event) to MedImmune and discussed with the medical monitor.

6.4 Safety Management During the Study

The MedImmune medical monitor has primary responsibility for the ongoing medical review of safety data throughout the study. This includes review of SAEs and timely review of AEs and “other events” reported during the study. MedImmune Patient Safety is responsible for the receipt, immediate review, investigation, and follow-up of SAEs reported from the clinical study sites.

A study-specific Dose-Escalation Committee will provide ongoing safety surveillance of the study, with regularly scheduled reviews of safety and other relevant data. This committee will be responsible for dose-escalation decisions and making recommendations regarding further conduct of the study. The Dose-Escalation Committee includes the MedImmune medical monitor for the study, the MedImmune Patient Safety physician for the study, and the principal investigator from each actively enrolling study site. This committee will review data, including all AEs, laboratory parameters, PK, and pharmacodynamic data, following the full enrollment of any dose-escalation cohort and completion of the DLT evaluation period. This committee will also review data at other time points in response to AEs assessed as medically relevant by the medical monitor. Dose-escalation decisions and outcomes of reviews of safety and other relevant data will be communicated to the MedImmune safety review committee. The sponsor will notify sites when enrollment into each dose cohort has been completed and when enrollment into the next dose cohort is permitted.

A MedImmune safety review committee provides safety surveillance, guidance, and oversight for all clinical development studies in which MedImmune has sponsor accountabilities. Committee members include, but are not limited to, appropriate representatives from Patient Safety, Clinical Development, and Regulatory Affairs. The committee reviews protocol-specific safety data and assesses changes to the benefit/risk profile of the molecule during early phases of development. Based on review of safety data,

the committee may suspend enrollment or subject dosing in clinical studies, request modification of study documents, or take other actions as deemed necessary.

6.4.1 Interruption or Permanent Discontinuation of Study Dosing in Individual Subjects

Dosing of MEDI-551 may be interrupted for up to 4 hours in subjects experiencing Grade 2 or 3 infusion reactions as described in Section 4.5.2.

An individual subject will not receive any further investigational product (i.e., permanent discontinuation) if any of the following occur in the subject in question:

1. Withdrawal of consent;
2. Allergic reactions \geq Grade 2 or any allergic reaction that necessitates the use of systemic pressors.
 - Grade 3 infusion reactions that do not respond to medical therapy (including interruption of infusion for \leq 4 hours) or that occur despite steroid prophylaxis. Any Grade 4 infusion reaction or any infusion reaction that necessitates the use of systemic pressors.
3. Grade 3 infusion reactions that respond to medical therapy or slowing the infusion rate and that are of limited duration will not necessitate dose interruption or discontinuation.
4. Pregnancy;
5. DLT (see Section 4.5.6 for definition of DLTs). The Medical Monitor may decide that certain events meeting the criteria for DLT are controllable and that retreatment is considered safe.
 - a. Subjects whose DLT resolves to \leq Grade 1 or baseline within 7 days can be retreated during the DLT period at one dose level below the subject's prior dose for all arms of the study except the first dose-escalation cohort of Arms B and C.
 - b. Subjects with toxicities considered DLTs that persist beyond 7 days will not be retreated for Arm A only.
 - c. Recurrence of the DLT following retreatment will necessitate permanent discontinuation of treatment with MEDI-551 for Arm A only.
6. Delay in administration of MEDI-551 for more than 21 days for reason of toxicity within any 3 consecutive cycles for Arm A or delay in cycles as dictated in Section 6.4.1 for Arms B, C, and D;
7. Recurrence of any \geq Grade 3 toxicity not attributable to other causes unless otherwise specified in Section 6.4.1;
8. Documentation of disease progression;
9. Any event which, in the opinion of the investigator, contraindicates further dosing such as intercurrent illnesses, significant drug toxicities or complications if judged by the investigator to be in the best interest of the subject;
10. Subject non-compliance;

11. Treatment with another investigational agent;
12. Initiation of alternative anticancer therapy;
13. Achievement of a CR and a maximum of 2 additional cycles after CR. For the purposes of discontinuation of drug, CR shall be defined as the time of hematological and radiological CR without necessity of BM confirmation.

Subjects who are permanently discontinued from investigational product will be followed for safety for approximately 90 days post last dose. In addition, until Version 13.0, subjects were to be followed for disease evaluation every 3 months after the 90-Day Post Last Dose Visit until disease progression, death, initiation of alternative therapy, withdrawal of consent, or end of study. Upon disease progression, subjects were to be followed only for survival every 3 months until death, withdrawal of consent, or end of study.

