Grade 3 or 4 ^{b, c}	
First Occurrence:
 
 • For AEs present before the next dose of MEDI-551 is to be given, delay next dose of MEDI-551 for up to 7 days until resolution to ≤ Grade 1 or baseline, and resume at 50% of current dose level. • If next dose is delayed for > 7 days due to failure of toxicity to resolve to ≤ Grade 1 or baseline, discontinue MEDI-551. • For Grade 3 infusion reaction, infusion rate may be decreased by 50% or interrupted for up to 4 hours and symptomatic care instituted as clinically indicated; steroid prophylaxis must be employed for all subsequent doses of MEDI-551. Following interruption, infusion should be resumed at 50% of original rate for remainder of infusion. For Grade 3 infusion reaction that does not respond to medical therapy (including interruption of infusion for ≤ 4 hours) or that occurs despite steroid prophylaxis, permanently discontinue MEDI-551. • For any Grade 4 infusion or allergic reaction that necessitates the use of systemic pressor agents, permanently discontinue MEDI-551. 
Second Occurrence:
 
 • Permanently discontinue MEDI-551.

See Section 6.4.1 for additional details on dose interruption and study discontinuation criteria.

^a Hematologic abnormalities equal in severity to the subject’s baseline and lymphopenia (any grade) do not require dose modification.

^b Except Grade 3 or 4 toxicities noted as exceptions to the DLT criteria (see Section 4.5.6).

^c For ≥Grade 3 hematologic toxicities other than lymphopenia, resolution to ≤ Grade 2 or subject’s baseline is required to re-initiate treatment.

Arms B, C, and D

During the DLT period, dose modification was not permitted. However, a delay in therapy due to reversible non-DLT toxicity was permitted as long as the total delay within the cycle is ≤ 7 days total. Any toxicity leading to a delay > 7 days in duration during the DLT period was considered a DLT.

Following the DLT period, subsequent cycles of MEDI-551 could be delayed or modified based on hematologic and nonhematologic toxicities observed during each subsequent cycle of treatment as described in Table 4.5.2.1-2. Both hematologic and nonhematologic toxicities were graded according to the NCI CTCAE V4.03 ([CTCAE, 2010](#)).

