Grade 3 or 4 ^{a,b}	
First Occurrence:
 
 • For AEs present before the next dose of MEDI-551 is to be given, delay next dose of MEDI-551 for up to 7 days until resolution to ≤ Grade 1 or baseline, and resume at 50% of current dose level. • If next dose is delayed for > 7 days due to failure of toxicity to resolve to ≤ Grade 1 or baseline, permanently discontinue MEDI-551. • For Grade 3 infusion reaction, infusion must be stopped for up to 4 hours until the subject recovers. An additional dose of steroids will be given and the infusion may resume but the infusion rate must be decreased by 50% for remainder of infusion. For Grade 3 infusion reaction that does not respond to medical therapy (including interruption of infusion for ≤ 4 hours) or that occurs despite steroid prophylaxis, discontinue MEDI-551. • For any Grade 4 infusion or allergic reaction that necessitates the use of systemic pressor agents, permanently discontinue MEDI-551. 
Second Occurrence:
 
 • For AEs present before the next dose of MEDI-551 is to be given, permanently discontinue MEDI-551.
Hematologic Toxicity ^{c,d}	
Grade 1 or 2	None
Grade 3 ^{a,b}	
First Occurrence:
 
 • Delay dose by up to 7 days until resolution to ≤ Grade 2 and resume at current dose level. If subject does not recover to ≤ Grade 2 within that time, permanently discontinue MEDI-551. 
Second Occurrence:
 
 • Delay dose by up to 7 days until resolution to ≤ Grade 2 and decrease dose by 50%. If subject does not recover to ≤ Grade 2 within that time, permanently discontinue MEDI-551. 
Third Occurrence:
 
 • Permanently discontinue MEDI-551.
Grade 4 ^{a,b}	
First Occurrence:
 
 • Delay dose by up to 7 days until resolution to ≤ Grade 2 and decrease dose by 50%. If subject does not recover to ≤ Grade 2 within that time, permanently discontinue MEDI-551. 
Second Occurrence:
 
 • Permanently discontinue MEDI-551.

See Section 6.4.1 for additional details on dose interruption and study discontinuation criteria.

- ^a Except Grade 3 or 4 toxicities noted as exceptions to the Dose Limiting Toxicity (DLT) criteria (see Section 4.5.6).

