All subjects must receive mandatory premedication consisting of a minimum dose of 60 mg of IV methylprednisolone (or its equivalent) as well as 500 to 650 mg oral acetaminophen (or

paracetamol equivalent) and 50 mg IV diphenhydramine (or its equivalent) before the start of the initial MEDI-551 infusion. The initial infusion of MEDI-551 will be administered a minimum of 30 to 60 minutes after administration of mandatory premedications (as described in this section) according to the following sequence of infusion rates, regardless of dosage form:

- 1 mL/minute for a minimum of 15 minutes, then
- 2 mL/minute for a minimum of 15 minutes, then
- 4 mL/minute to complete the infusion

The minimum infusion time will be 81 minutes. Subjects receiving doses ≥ 24 mg/kg in Arm B will receive the initial infusion over 2 days on Day 1 and Day 2 of Cycle 1. The Day 1 infusion will be administered over a minimum of 81 minutes as described above. The Day 2 infusion will be administered over a minimum of 60 minutes (+ 15 minutes at the investigator's discretion). If the subject experiences an infusion reaction on Day 1, the Day 2 infusion will be administered over a minimum of 90 minutes. Subjects will be monitored closely during the initial infusion of MEDI-551, with vital signs recorded every 5 minutes over the first 30 minutes of the infusion and then every 15 minutes for the remainder of the infusion duration. Additional details regarding vital signs monitoring during the initial infusion of MEDI-551 are provided in Section 6.4.3. For subsequent infusions, MEDI-551 will be administered over 60 minutes (+ 15 minutes at the investigator's discretion). Vital signs will be monitored as described in Section 6.4.3. The initial infusion of MEDI-551 will be administered on Day 1 of Cycle 1 for Arms B and D, and Day 2 of Cycle 1 for Arm C.

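### In Arms B, C and D the protocol is inconsistent on a brief, responding Grade 3 infusion reaction: whether to pause, how fast to restart and, after steroid prophylaxis, whether to discontinue

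*Protocol*

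**What the plan says.** Section 6.4.1 opens with a permissive line: "Dosing of MEDI-551 may be interrupted for up to 4 hours in subjects experiencing Grade 2 or 3 infusion reactions". It refers to Section 4.5.2 for the description. A numbered list of reasons for permanent discontinuation follows.

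- Item 2 includes Grade 3 infusion reactions that fail medical therapy or that arise despite steroid prophylaxis.
- Item 3 covers "Grade 3 infusion reactions that respond to medical therapy or slowing the infusion rate" and says that those "that are of limited duration will not necessitate dose interruption or discontinuation". It names no arm.

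For Arms B, C and D, Table 4.5.2.1-2 (Section 4.5.2.1) says: "For Grade 3 infusion reaction, infusion must be stopped for up to 4 hours until the subject recovers". It then provides for extra steroids and resumption at half rate. It ends with a clause for a Grade 3 reaction that does not respond "or that occurs despite steroid prophylaxis, discontinue MEDI-551". The note under the table reads: "See Section 6.4.1 for additional details on dose interruption and study discontinuation criteria".

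For the same arms, Sections 4.5.3 and 6.4.3 allow, but do not require, interruption for an infusion reaction. Restart is at 1 mL/minute, with optional increases of 50% every 15 minutes. Section 4.5.3 also states, for these arms: "All subjects must receive mandatory premedication consisting of a minimum dose of 60 mg of IV methylprednisolone". That premedication applies before the initial MEDI-551 infusion; Sections 4.5.4 and 6.4.3 repeat it.

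For Arm A, Table 4.5.2.1-1 says: "For Grade 3 infusion reaction, infusion rate may be decreased by 50% or interrupted for up to 4 hours".

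**The concern.** A site in Arms B to D treating a Grade 3 infusion reaction that settles quickly can find three statements about pausing the infusion: required, optional and not needed. If the subject had been premedicated with steroids, the site can also find both an instruction to discontinue MEDI-551 and a statement that discontinuation is not needed.

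This bears on subject safety and on the data. The choice affects exposure and the number of discontinuations attributed to infusion reactions. It also affects reporting, because Sections 6.1.3.2 and 6.3.5.5 require notification within 24 hours when an infusion reaction ends treatment for good. Safety is a primary endpoint in Arms B and C and a secondary endpoint in Arm D. Section 1.6 names infusion reactions as an identified risk of MEDI-551. The situation is not hypothetical: the Version 12.0 entry in Section 15 records Grade 3 infusion-related reactions during the first infusion in 2 of 3 subjects at 6 mg/kg, and describes corticosteroid prophylaxis as an existing safeguard.

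**Working it through.** The protocol gives no figure to reproduce. The check sets the current passages side by side for Arms B to D.

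**1. Do the passages concern the same action and the same subjects?**

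- *Action.* The opening line of 6.4.1 uses interruption for an infusion pause of up to 4 hours. That is the action in the table, so item 3 cannot be confined to delays of later doses.
- *Subjects.* Items 5 and 6 of the same list name arms where a rule is arm-specific. Item 3 names none, so it covers Arms B to D.
- *Precedence.* Section 6.4.1 refers to Section 4.5.2 for interruption, and the table note refers back to 6.4.1. Neither is said to govern.

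**2. Instructions for a responding, brief Grade 3 reaction, Arms B to D**

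| Place | Pause | Restart rate |
|---|---|---|
| Table 4.5.2.1-2 | required | halved for the rest of the infusion |
| 6.4.1 item 3 | not needed | none given |
| 4.5.3 and 6.4.3 | optional | 1 mL/minute, then optional 50% steps every 15 minutes |

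**3. Size of the restart difference.** Section 4.5.3 sets the initial infusion at 1, then 2, then 4 mL/minute. Assume that the table's halving applies to the rate running when the reaction began; the table does not say.

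- Reaction at 1 mL/minute: table 1 × 0.5 = 0.5; Sections 4.5.3 and 6.4.3 give 1.
- Reaction at 2 mL/minute: table 2 × 0.5 = 1; the sections also give 1, but allow later increases.
- Reaction at 4 mL/minute: table 4 × 0.5 = 2; the sections give 1, then up to 1 × 1.5 = 1.5 after 15 minutes and 1.5 × 1.5 = 2.25 after 30 minutes.

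The two rules agree at restart in only one of the three steps, and neither is uniformly the slower.

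**4. Which Grade 3 reactions meet conflicting text?**

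- *Not responding, with or without prophylaxis.* Item 2 and the table both call for discontinuation, and item 3 does not apply. There is no conflict on discontinuation.
- *Responding and brief, no prophylaxis.* There is conflict on the pause and the restart rate. No passage cited here calls for discontinuation.
- *Responding and brief, despite prophylaxis.* Item 2 and the table call for discontinuation. Item 3 has no prophylaxis exception and says discontinuation is not needed. The conflict is on discontinuation itself.

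The third group includes every responding, brief Grade 3 reaction at the first MEDI-551 infusion in these arms, because premedication is compulsory there.

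**5. Reach.** Enrollment in Arms B, C and D was 7 + 19 + 16 = 42. Enrollment closed on 30Sep2015. On 19Jan2017, 9 subjects remained on treatment across the study, all treated for at least 1 year; their arms are not stated.

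**The case against.** The strongest reply is that the passages can be read together. Item 3 says only that interruption is not needed and does not forbid it, so a site that pauses under the table breaches nothing in 6.4.1. The opening line of 6.4.1 defers to Section 4.5.2, which suggests that the arm-specific tables govern. On reactions despite prophylaxis, item 2 and the table agree. The route of stopping, treating and resuming still has cases to cover: a first Grade 3 reaction at a later infusion without premedication. Section 4.5.6 draws a similar line, excepting from the DLT definition in Arms B and C certain first Grade 3 reactions without steroid prophylaxis. Item 3 can then pass as a misnumbered exception to item 2.

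Much of this stands. Required against not needed is an inconsistency, not a pair of opposite commands. The list placement alone is editorial, since nobody would take item 3 as a trigger for discontinuation.

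Two parts do not stand. The deference to Section 4.5.2 is undone by the table's reference back to 6.4.1, and Sections 4.5.3 and 6.4.3 add a third wording. Nor does reading item 3 as an exception to item 2 resolve the prophylaxis case. If item 3 qualifies item 2, a responding, brief reaction despite prophylaxis does not end treatment under 6.4.1, contrary to the table. If item 2 prevails, it does, contrary to the words of item 3. The text does not choose.

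**Conclusion.** The inconsistency is real but narrow. It concerns Arms B, C and D and Grade 3 infusion reactions that respond and are brief. For these, the text disagrees on the pause and the restart rate and, where steroid prophylaxis was given, on discontinuation.

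A reader might infer more, and the documents do not support it:

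- *Opposite instructions throughout.* Only the discontinuation conflict comes close to that; on pausing, 6.4.1 does not forbid what the table requires.
- *Arm A as a further conflicting rule.* Its table permits slowing or interruption and is compatible with 6.4.1 on interruption. Different rules for different arms are not in themselves a contradiction.
- *Every first-infusion Grade 3 reaction in Arms B to D is affected.* Those that do not respond meet consistent text on discontinuation.
- *Infusion reaction as the drug's main risk.* The protocol calls it an identified risk and does not rank it as the main one.
- *A continuing hazard at first infusions.* With enrollment closed and every remaining subject treated for at least 1 year, no first infusions remain. Version 13.0 also ends re-treatment of subjects who relapse after CR.

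Looking forward, the point can affect at most those of the 9 subjects who belong to Arms B to D, at later infusions. Looking back, it can affect how infusion-reaction discontinuations are read among at most 42 subjects. That figure is a ceiling: the protocol does not give the number with such reactions, and the wording in force when each was treated cannot be confirmed from the current text. Nor does the protocol say how the clauses were applied to the two subjects at 6 mg/kg, so no mishandling can be inferred.

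**What to change.** The sponsor should reconcile Table 4.5.2.1-2, Section 4.5.3 (Arms B, C and D), Section 6.4.1 items 2 and 3, and Section 6.4.3 so that they give:

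- one instruction on pausing and one on the restart rate for a Grade 3 infusion reaction in these arms;
- one statement of how the clause on reactions despite steroid prophylaxis applies where premedication is mandatory;
- an explicit order of precedence in place of the circular references between 6.4.1 and the table.

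Item 3 should move out of the numbered list of permanent-discontinuation triggers. Which clinical rule should prevail is for the sponsor and investigators to decide; no view is given here.

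The cost is amendment wording or a clarification letter. Sample size, endpoints and data collection are untouched.
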